5.6.1.2. Patient's Global Impression of Change (PGIC) of Severity of Ulcerative Colitis

Participants' perceived change (improvement or deterioration) in the severity of their UC will be assessed using the **PGIC**. Participants will rate how their UC has changed since the beginning of the study using a 7-point scale ranging from "a lot better now" to "a lot worse now" with a neutral center point ("neither better nor worse").

5.6.2. Estimands

Unless otherwise specified, the attributes and strategies for the ICEs that were used for the primary estimand of the primary endpoint (Estimand 1, Section 5.3.2) will also be used for the estimand for each exploratory efficacy endpoint (Section 5.6).

ICE categories 1-3 will be handled by the **composite strategy**. ICE category 4 will be handled by the **hypothetical strategy** (as if participants would have not experienced this intercurrent event), and ICE category 5 will be handled by the **treatment policy strategy**. To be specific,

- Participants with an ICE in category 1-3 prior to a visit will be considered, at that visit and all subsequent visits, as **not having achieved the binary endpoints for binary endpoints** and as **having no change from baseline (i.e., the baseline value will be assigned) for continuous and ordinal endpoints**.

- PGIC has no baseline data. When PGIC is analyzed as an ordinal endpoint, participants with an ICE in category 1-3 prior to a visit will be considered to have a UC severity change of “neither better, nor worse (no change)” from that visit onwards.
- Participants with an ICE 4 will have their observed data set to missing at all visits after the ICE 4.
- Participants with an ICE 5 will have their observed data used after the ICE 4 used, if available.
- For participants experiencing multiple ICEs, ICEs in categories 1-3 will override ICEs 4 and 5.

5.6.3. Estimators (Analyses) for Estimands

Unless otherwise specified, exploratory endpoints presented in Section 0 will be analyzed based on the FAS (Section 2.2.2) according to randomized study intervention regardless of the study intervention actually received.

Descriptive statistics (i.e., mean, median, SD, IQ range, minimum, and maximum) will be used to summarize continuous endpoints and counts and percentages will be used to summarize binary endpoints by visit.

Treatment comparisons between combination therapy versus each monotherapy will be performed by visit through Week 38. No adjustment for multiple comparisons will be made for these other endpoints. Nominal p-values will be presented.

Binary Endpoints

After accounting for the ICEs, participants with missing status for a binary endpoint will be considered not to have achieved the associated binary endpoint (i.e. nonresponder imputation). Treatment comparisons (combination therapy versus each monotherapy) will be performed using analyses suitable for categorical data (e.g., a CMH chi-square test stratified by corticosteroid use at baseline, as appropriate) to compare the proportion of participants achieving the endpoints. In case of rare events, the Fisher’s exact test will be used for treatment comparisons.

Continuous Endpoints

After accounting for the ICEs, to account for the missing data for continuous endpoints, a MMRM as described in Section 5.5.3 will be used, under the assumption of MAR, to test the treatment comparison between combination therapy versus each monotherapy. In MMRM, missing data will not be imputed, but rather missing data will be accounted for through correlation of repeated measures in the model. If the normality assumption is in question, an appropriate transformation may be implemented before fitting the MMRM model.

Ordinal Endpoints

After accounting for the ICEs, treatment comparisons (combination therapy versus each monotherapy) will be performed using a CMH chi-square test (Row Mean Scores) stratified by corticosteroid use at baseline (yes, no).

6. SAFETY

Safety data, including but not limited to, AEs, serious adverse events (SAEs), infections, serious infections, and changes in laboratory assessments will be summarized through Week 12 and through Week 38. Treatment-emergent AEs will be summarized by treatment group and Medical Dictionary for Regulatory Activities (MedDRA) system organ class and preferred terms.

Unless otherwise specified, safety analyses will be provided for participants in the Safety Analysis Set, which includes all randomized participants who received at least 1 dose of study intervention, according to the study intervention that they actually received, regardless of the study intervention they were randomized to. No formal statistical comparisons are planned.

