
CRP=C-reactive protein; C-SSRS=Columbia-Suicide Severity Rating Scale; Early Term=early termination visit; IBDQ=Inflammatory Bowel Disease Questionnaire; PBMC= peripheral blood mononuclear cell; PK=pharmacokinetic; PGIC=Patient’s Global Impression of Change (of Severity of UC); PRO=patient-reported outcome; PROMIS=Patient-Reported Outcomes Measurement Information System; RNA=ribonucleic acid; TB=tuberculosis; UC=ulcerative colitis; W=Week.
 
a. Visit dates are based on the participant’s original randomization date; visit windows are as follows: day of the scheduled visit ±4 days (ie, plus or minus 4 days).
 
b. All assessments are to be completed before study intervention administration, unless otherwise specified; PRO assessments should be completed first. When blood samples are to be collected for safety, PK, efficacy, and biomarkers evaluations at the same time point, the order of blood draws will be samples for CRP, hematology and chemistry, PK/immunogenicity, serum biomarkers, and whole blood RNA.
 
c. Participants who discontinue study intervention or terminate study participation after Week 12 should undergo the procedures indicated for an Early Term visit.
 
d. Participants, including those who discontinue study intervention administration (but have not terminated study participation), will have a final safety follow-up visit approximately 16 weeks after the last administration of study intervention.
 
e. At their last study visit, each study participant will be invited to complete an Independent Ethics Committee/Institutional Review Board approved Experience Survey, to share to his/her experience as a volunteer in this study. The responses will be collected by an external party and provided anonymously to the sponsor.
 
f. Endoscopy findings will be assessed by the investigator (ie, local endoscopist) during the procedure and a video of the endoscopy must be submitted to the central reader.
 
g. If TB is suspected at any time, a chest radiograph (or chest CT scan if obtained instead) and QuantiFERON[®]-TB test should be performed. In countries where the QuantiFERON[®]-TB test is not registered/approved or the tuberculin skin test is mandated by local health authorities, TB skin testing (see Appendix 3 [Section 10.3]) should also be performed. Note: In Ukraine, while the QuantiFERON[®]-TB test is not approved/registered, it is accepted and a tuberculin skin test is not required.
 
h. Temperature, pulse/heart rate, respiratory rate, and blood pressure. At a study intervention administration visit, vital sign measurements should be obtained before and approximately 30 minutes after study intervention administration or if the participant reports any symptoms.
 
i. Must be performed before any study intervention administration for female participants of childbearing potential.
 
j. The C-SSRS should be completed after all PROs and before any other tests, procedures, or other consultations to prevent influencing participant perceptions.
 
k. Samples should be collected before any study intervention administration. All reasonable attempts should be made to collect samples at the scheduled timepoints and record the actual dates and times of PK sample collections.
												

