Given the risk of serious infections associated with the anti-TNF class and combination biologic use, the eligibility criteria and screening assessments of this study are designed to exclude subjects with chronic/active infections or a predisposition to infections. Measures to ensure the early detection of TB, such as chest radiograph and QuantiFERON[®]-TB test, are outlined in Section 8.2.12 and participants with a history of latent or active TB are excluded from this study. Subjects older than 65 years of age are excluded from the study due to immunosenescence, which is defined as the state of dysregulated immune function that contributes to an increased susceptibility of the elderly to infection.^{8,41} In contrast to the reported longer duration RA combination biologics studies (ie, up to 1 year),^{17,67,68} the combination comparison phase of this study in UC is of relatively short duration (ie, approximately 12 weeks), meaning that participants randomized to the combination therapy intervention group will only receive 3 doses of guselkumab and 4 doses of golimumab that overlap. To reduce the risks associated with immunosuppression, immunomodulators (6-MP, AZA, and MTX) must be discontinued for at least 2 weeks before the first administration of study intervention. Additionally, participants taking more than 20 mg of prednisone or equivalent are excluded from the study, and there will be mandatory oral corticosteroid tapering beginning at Week 6. Participants will be closely monitored for signs and symptoms of infection during and after treatment. During the combination comparison phase, clinic visits are scheduled biweekly. Furthermore, safety will be monitored in the first 25 participants, randomized to any intervention group and treated on an ongoing basis, for any potential safety concerns that would result in a pause in dosing by an independent Data Monitoring Committee (DMC). Details about the evaluation of this initial cohort and subsequent DMC reviews are outlined in Section 9.5.1. Safety evaluations will include AEs, clinical laboratory tests (hematology and chemistry), vital signs and physical examinations, a screening electrocardiogram (ECG), hypersensitivity reactions, AEs temporally associated with infusion, injection-site reactions, and early detection of active TB. The safety follow-up period for this study is 16 weeks after the last dose of study intervention.

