8.3. Adverse Events and Serious Adverse Events

Timely, accurate, and complete reporting and analysis of safety information from clinical studies are crucial for the protection of participants, investigators, and the sponsor, and are mandated by regulatory agencies worldwide. The sponsor has established Standard Operating Procedures in conformity with regulatory requirements worldwide to ensure appropriate reporting of safety information; all clinical studies conducted by the sponsor or its affiliates will be conducted in accordance with those procedures.

Adverse events will be reported by the participant (or, when appropriate, by a caregiver, surrogate, or the participant's legally acceptable representative) for the duration of the study.

Anticipated events will be recorded and reported as described in Appendix 10 (Section 10.10).

For further details on AEs and SAEs (Definitions and Classifications; Attribution Definitions; Severity Criteria; Special Reporting Situations; Procedures) as well as product quality complaints, refer to Appendix 9 (Section 10.9), Adverse Events: Definitions and Procedures for Recording, Evaluating, Follow-Up, and Reporting.

8.3.1. Time Period and Frequency for Collecting Adverse Event and Serious Adverse Event Information

All Adverse Events

All AEs and special reporting situations, whether serious or non-serious, will be reported from the time a signed and dated ICF is obtained until completion of the participant's last study-related procedure, which may include contact for follow-up of safety. Serious adverse events, including those spontaneously reported to the investigator within 16 weeks after the last dose of study intervention, must be reported using the Serious Adverse Event Form. The sponsor will evaluate any safety information that is spontaneously reported by an investigator beyond the time frame specified in the protocol.

Serious Adverse Events

All SAEs occurring during the study must be reported to the appropriate sponsor contact person by study-site personnel within 24 hours of their knowledge of the event.

Information regarding SAEs will be transmitted to the sponsor using the Serious Adverse Event Form, which must be completed and signed by a physician from the study site, and transmitted to the sponsor within 24 hours. The initial and follow-up reports of a SAE should be made by facsimile (fax).

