Figure 1: Schematic Overview of Study CNTO1959UCO2002

Immunomodulators (6-MP, AZA, and methotrexate [MTX]) must be discontinued for at least 2 weeks before the first dose of study intervention. For participants who are receiving oral corticosteroids at baseline, the investigator must begin tapering the daily dose of corticosteroids at Week 6. The use of concomitant and prohibited therapies is described in Protocol Section 6.5. In general, doses of concomitant therapies for UC should remain stable through Week 38 (except for mandatory oral corticosteroid tapering beginning at Week 6), and concomitant therapies for UC should not be initiated unless considered medically necessary by the investigator. Initiation of prohibited therapies will result in discontinuation of study intervention.

All participants will be evaluated for clinical worsening of UC throughout the study. Endoscopy with central read is planned for screening/baseline, Week 12, and Week 38. Consenting participants will have an additional endoscopy at Week 4, which will also be assessed by a central reader. Efficacy, PK and PD parameters, biomarkers, and safety will be assessed according to the Schedule of Activities (SoA) (Protocol Section 1.3). A pharmacogenomic blood sample will be collected from participants who consent to this component of the protocol (where local regulations permit). Participation in pharmacogenomic research is optional.

Overall participant duration will be up to 58 weeks total (screening: up to 8 weeks; treatment duration: 38 weeks [12 weeks for the combination comparison phase; 26 weeks for the monotherapy phase]; safety follow-up: approximately 16 weeks after the last administration of study intervention at Week 34).

An interim analysis (IA) was performed in April 2020 to inform future clinical development planning after the first 126 randomized participants (i.e., 60% of the planned sample size) who received at least one administration of study intervention (complete or partial) completed the Week 12 assessments or terminated study participation prior to the Week 12 visit. The details regarding this IA are provided in the Interim Analysis Plan (IAP).

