There are 3 planned database locks (DBLs) for this study, respectively, at Week 12, at Week 38, and at end of the study. The end of the study is defined as when the last participant completes his or her final safety follow-up visit. The first DBL will occur when all participants randomized in this study have either completed the Week 12 assessments or terminated study participation prior to the Week 12 visit (referred to as Week 12 DBL hereafter). The second DBL will occur when all participants randomized in this study have either completed the Week 38 assessments or terminated study participation prior to the Week 38 visit (referred to as Week 38 DBL hereafter). The third DBL will occur at end of study when all participants randomized in this study have either completed their final safety follow-up visit or have terminated study participation [referred to as Final Safety DBL hereafter].

The primary endpoint of this study is clinical response at Week 12 (refer to Section 5.3 for endpoint definition and analyses). The major secondary endpoint is clinical remission at Week 12 (Section 5.4 – definitions and analyses methods). The primary and major secondary endpoints will be analyzed at the Week 12 DBL.

An external independent data monitoring committee (DMC) will be commissioned for this study to monitor the safety of the study in an unblinded fashion on a regular basis and whenever deemed necessary. Refer to the DMC charter for more details on the DMC.

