Treatment assignment blinding will be maintained for study sites, site monitors, and participants until the analyses based on the Final Safety DBL are completed. The full sponsor unblinding will occur after the Week 38 DBL. A limited number of sponsor personnel were unblinded to the IA data (only those randomized participants who were included in the IA; the treatment assignment for the remaining participants remained blinded) for data analyses and review. The sponsor personnel who were unblinded to the IA data were documented in the IA unblinding plan. In addition, a limited number of sponsor personnel will become unblinded at the Week 12 DBL for data analyses and review. Identification of sponsor personnel who will have access to the unblinded data and at what level (treatment group-level or participant-level) will be documented in the unblinding plan before unblinding occurs at the Week 12 DBL.

The investigator will not be provided with randomization codes. The codes will be maintained within the IWRS, which has the functionality to allow the investigator to break the blind for an individual participant.

Under normal circumstances, the investigator blind should not be broken unless specific emergency treatment/course of action would be dictated by knowing the treatment status of the participant. In such cases, the investigator may in an emergency determine the identity of the treatment via the IWRS. It is recommended that the investigator contact the sponsor or its designee, if possible, to discuss the particular situation before breaking the blind. Telephone contact with the sponsor or its designee will be available 24 hours per day, 7 days per week. If the blind is broken, the sponsor must be informed as soon as possible. The date and reason for the unblinding must be documented in the appropriate section of the eCRF and in the source document. The documentation received from the IWRS indicating the code break must be retained with the participant's source documents in a secure manner.

Additionally, a given participant's treatment assignment may be unblinded to the sponsor, the Independent Ethics Committee/Institutional Review Board (IEC/IRB), and site personnel to fulfill regulatory reporting requirements for suspected unexpected serious adverse reactions (SUSARs). If a participant is unblinded for this reason, the information must be entered in the appropriate section of the eCRF and in the participant's source documents.

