6.1. Adverse Events

The verbatim terms used in the eCRF by investigators to identify AEs will be coded using the Medical Dictionary for Regulatory Activities (MedDRA). Treatment-emergent AEs (TEAEs) are AEs with onset during the intervention phase or that are a consequence of a pre-existing condition that has worsened since baseline. All reported AEs which are treatment-emergent will be included in the analysis. For each AE, the count and percentage of participants who experience at least 1 occurrence of the given event will be summarized by intervention group.

The following analyses of TEAEs will be used to assess the safety of participants:

- Frequency and type of AEs
- Frequency and type of SAEs
- Frequency and type of reasonably related AEs as assessed by the investigator
- Frequency and type of AEs leading to discontinuation of study intervention
- Frequency and type of infections (including COVID-19 infections)
- Frequency and type of serious infections
- Frequency and type of infections requiring oral or parenteral antimicrobial treatment
- Frequency and type of AEs temporally associated with infusion
- Frequency and type of injection-site reactions

Since safety should be assessed relative to exposure and follow-up, all AE summary tables will summarize the average weeks of follow-up and average exposure (number of administrations) for each treatment group.

In addition to the summary tables, a by-subject listing will be provided for deaths that occurred during the study and, respectively, for the following TEAEs:

1. SAEs
2. AEs that led to permanent discontinuation of study intervention
3. Serious infections including TB
4. COVID-19 infections
5. Anaphylactic reactions or serum sickness reactions
6. Malignancies

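### SAP 6 ends its named safety summaries at Week 38, about 12 weeks before AE collection ends for participants dosed at Week 34; separately, the haemoglobin-increase grading row does not work as printed

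*SAP*

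**What the plan says.** **Summaries.** SAP 6 covers AEs, SAEs, "infections, serious infections, and changes in laboratory assessments will be summarized through Week 12 and through Week 38". No later window for AEs, SAEs or infections is named anywhere in the SAP.

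**Collection.** Protocol 8.3.1 has AEs reported from consent until the participant's "last study-related procedure, which may include contact for follow-up of safety". Footnote d to Table 2 of the Schedule of Activities says that participants, including those who stop treatment early, "will have a final safety follow-up visit approximately 16 weeks after the last administration of study intervention". The same table schedules AE collection at that visit. SAP 1.2 gives "safety follow-up: approximately 16 weeks after the last administration of study intervention at Week 34". Protocol 2.3 includes this period among its safety measures: "The safety follow-up period for this study is 16 weeks after the last dose of study intervention".

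**Locks.** SAP 1.2 plans a last lock: "The third DBL will occur at end of study when all participants randomized in this study have either completed their final safety follow-up visit". Participants who left early count as finished. SAP 1.5 keeps sites and participants blinded "until the analyses based on the Final Safety DBL are completed". Neither section says which tables those analyses contain.

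**Treatment-emergent events.** SAP 6.1 states: "Treatment-emergent AEs (TEAEs) are AEs with onset during the intervention phase", or that reflect a pre-existing condition that has worsened. Protocol 9.4.2 uses the same definition. Neither says when the intervention phase ends.

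**Resource use.** In SAP 9, two of the three bullets describe Week 38 as the final safety follow-up. The surgery bullet does not. Protocol 3.2.3 gives Week 38 alone.

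**Haemoglobin grading.** SAP Attachment 7 prints the haemoglobin-increase grades as above 0 to 2 times the upper limit of normal (ULN), above 2 to 4 times ULN, and above 4 times ULN.

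**The concern.** The protocol collects AEs to about Week 50, but the SAP's stated cut-off is Week 38. An analyst who follows SAP 6 to the letter would produce no table containing an SAE or infection that began at, say, Week 45.

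The by-subject listings do not clearly make up for this. They carry no calendar limit, but apart from deaths they list treatment-emergent events, and the end of the treatment-emergent period is undefined. If it ends at Week 38, a new serious infection or malignancy in follow-up drops out of the listings as well. If it runs to the last visit, the listings catch the event but the summaries still do not.

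The safety of combination therapy followed by guselkumab is a stated secondary objective, and golimumab monotherapy continues to Week 34, so follow-up after the last dose is part of what the trial set out to describe.

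The haemoglobin row is a separate matter. Haemoglobin enters the maximum-grade summary, the shift tables and the listing of values at Grade 2 or above (SAP 6.2), so a faulty row feeds all three.

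**Working it through.** **The plan's own figure.** SAP 1.2 gives up to 58 weeks per participant.
- Screening 8 + last administration at Week 34 + follow-up 16 = 58, an exact match.
- Counting follow-up from Week 38 instead gives 8 + 38 + 16 = 62, which does not match.

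Follow-up therefore runs from Week 34.

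**Size of the gap, last administration at Week 34.**
- Final visit: 34 + 16 = Week 50.
- Weeks after the last named cut: 50 − 38 = 12.
- Share of post-baseline time: 12/50 = 24%.
- SAP Table 4 allows ±7 days for the final follow-up visit: 11/49 = 22% to 13/51 = 25%.
- Per arm of 70 with no dropout: 70 × 12/52 = 16.2 of 70 × 50/52 = 67.3 patient-years. At 13 weeks the gap is 70 × 13/52 = 17.5, so 16.2 is a nominal figure and not a ceiling.

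**Share of follow-up after the last active dose** (dosing weeks from Protocol 6.1).
- Guselkumab, Week 32: 12/(50 − 32) = 12/18 = 67%.
- Golimumab monotherapy, Week 34: 12/(50 − 34) = 12/16 = 75%.

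**Dependence on the last administration** (week + 16 − 38, not below 0).

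| Last administration | Follow-up visit | Weeks after Week 38 |
|---|---|---|
| Week 22 | Week 38 | 0 |
| Week 24 | Week 40 | 2 |
| Week 26 | Week 42 | 4 |
| Week 30 | Week 46 | 8 |
| Week 32 | Week 48 | 10 |
| Week 34 | Week 50 | 12 |

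**What Week 38 already covers in the combination arm.** The last golimumab dose in that arm is at Week 10 (SAP 1.2). Sixteen weeks later is Week 26. The Week 38 cut lies 38 − 10 = 28 weeks after that dose.

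**Not affected.** Routine laboratory data stop at Week 38 (SAP 6.2), so no laboratory summary is lost. Deaths are listed for the whole study (SAP 6.1).

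**Haemoglobin row.** All three cells are multiples of ULN, so they form one continuous scale that starts just above zero. Any value up to 2 × ULN is then a Grade 1 increase. A value of 9 g/dL is a Grade 1 increase and, by the decrease row (below 10.0 down to 8.0), also a Grade 2 decrease. The documents give no ULN. With an assumed ULN of 15 to 18 g/dL, Grade 2 begins above 30 to 36 g/dL and Grade 3 above 60 to 72 g/dL. The ALT, AST, alkaline phosphatase and bilirubin increase rows in the same attachment start above ULN.

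**The case against.** The best defence is that late events will be reported anyway. Protocol 6.3 and the SAP both plan a final safety lock with analyses, and Protocol 9.4.2 sets no Week 38 limit. SAP 6.1 puts every treatment-emergent AE into the analysis and reports average weeks of follow-up. Suicidality is summarised by the worst post-baseline outcome, with no end week given. SAP 9 may even show that the authors use Week 38 loosely to include the final follow-up. This stands as far as intent goes. A reader might infer from SAP 6 that events after Week 38 will be left out of the report, and the documents do not support that. They also do not name a single table for the final lock, and the sentence in SAP 6 sets an explicit limit. A loose label in SAP 9 that its own third bullet does not share cannot settle what SAP 6 means.

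A second objection concerns relevance. Protocol 2.3 discusses serious infection with combined biologics, and a reader might infer that the missing weeks hide the risk of the combination. They do not. Dual dosing ends at Week 10, the primary safety objective belongs to the first 12 weeks, and every arm is on monotherapy before the gap opens. This objection stands in full and limits the point to late follow-up.

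Third, participant protection does not depend on these tables. SAEs within 16 weeks of the last dose must be reported (Protocol 8.3.1), and the monitoring committee receives monthly SAE reports and unblinded safety tables at least every 3 months (Protocol 9.5.1). This also stands.

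On haemoglobin, SAP 6.2 says that grading follows CTCAE version 5.0, so programming from that source could avoid the fault. But the same section points to Attachment 7 for the criteria, and the printed row is what an analyst would follow.

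**Conclusion.** The point holds as an error of specification in the SAP. For participants dosed at Week 34, about 12 of 50 post-baseline weeks fall outside every named AE, SAE and infection summary. It would be wrong to apply that figure to everyone, because those who stopped earlier lose less or nothing. The figure assumes follow-up of 16 weeks from the last administration, as the 58-week total confirms. The patient-year figures also assume full arms and no dropout. No number of missed events can be given, because the documents state no event rate.

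The undefined end of the intervention phase is part of the same problem. The 38-week treatment duration and the separate follow-up column in Table 2 of the Schedule of Activities point towards Week 38, but the documents do not say so. The SAP 9 label is wrong under the planned schedule, since Week 38 and the final visit at about Week 50 are different time points.

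The haemoglobin-increase row is wrong as written but minor. It makes the increase lines in the maximum-grade and shift tables uninformative. It also keeps a real rise out of the Grade 2 listing unless the value exceeds twice ULN. Decrease grades and raw values are unaffected.

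**What to change.** 1. In SAP 6, keep the Week 12 and Week 38 cuts, which suit their phases. Add that AE, SAE and infection summaries, and the by-subject listings, will also be produced through the final safety follow-up visit at the Final Safety lock.
2. In SAP 6.1, state when the treatment-emergent period ends, for completers and for those who stop early, and align Protocol 9.4.2 with it. If it is meant to end at Week 38, give later AEs in a separate follow-up table.
3. In SAP 9, choose the time point intended and use it in all three bullets.
4. In Attachment 7, correct the haemoglobin-increase row against the CTCAE version 5.0 source, so that normal and low values are not graded as increases. The trial documents do not settle the bounds.

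The cost is small: existing AE programs are rerun at a lock already planned, one end point is defined, and one label and one table row are corrected. The downside is that some late events unrelated to treatment will enter the AE tables.
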